2.6 Health economics and/or patient reported outcomes

The following patient reported outcome exploratory endpoints are included in the trial:

Change from baseline to week 26 for:

- Health-related quality of life as evaluated by SF-36v2® Health Survey
- Treatment related impact as evaluated by the Treatment Related Impact Measure-Diabetes (TRIM-D)

Change from baseline to week 38 for:

- Health-related quality of life as evaluated by the SF-36v2® Health Survey
- Treatment related impact as evaluated by the TRIM-D

The domain and overall scores for both SF-36 and TRIM-D will be summarised descriptively based on observed data and explorative statistical analysis may be performed.

The data collected in the BHQ will not be included in the clinical trial report, nor will the data collected in the hypoglycaemic resource use interview questionnaire. Data from the latter will be used to assess costs associated with hypoglycaemia and provide information to be used in health economic analyses.

3 Changes to the statistical analyses planned in the protocol

3.1 Clarification of primary statistical analysis, primary estimand:

In the protocol version 4.0 the penalisation of data from subjects on treatment but with missing data at week 26 is only described in the sample size section, not in section 17.4 when describing the analysis in details. This is updated to clarify that also imputed values for subjects in IDegAsp arm on treatment for 26 weeks but with missing HbA_{1c} assessment at week 26 will be penalised.

Rationale:

Alignment of protocol sections.

3.2 Clarification of sensitivity analyses to secondary estimand for primary analysis,

The sensitivity analysis for the secondary estimand specified in the protocol version 4.0 includes subjects that complete the first 26 weeks of the trial on treatment and have on-treatment HbA_{1c} assessment at V28.

Rationale:

This is in alignment with the declared aim for the sensitivity analysis, namely to align with the phase 3a program.

3.3 Changes to supportive secondary endpoints and explorative endpoints

The following endpoints are considered secondary supportive and explorative endpoints, respectively:

Supportive secondary endpoints

Efficacy endpoints:

- Change from baseline in HbA_{1c}(%) after 38 weeks (defined as key supportive secondary efficacy endpoint in protocol)
- Change from baseline in fasting plasma glucose (FPG) after 26 weeks
- Change from baseline in fasting plasma glucose (FPG) after 38 weeks
- Responder (Yes/No) for HbA_{1c} after 26 weeks: HbA_{1c} < 7% (defined as key supportive secondary efficacy endpoint in protocol)
- Responder (Yes/No) for HbA_{1c} after 38 weeks: HbA_{1c} < 7% (defined as key supportive secondary efficacy endpoint in protocol)
- Responder (Yes/No) for HbA_{1c} after 26 weeks: HbA_{1c} < 7% without severe or BG confirmed symptomatic hypoglycaemia
- Responder (Yes/No) for HbA_{1c} after 38 weeks: HbA_{1c} < 7% without severe or BG confirmed symptomatic hypoglycaemia
- Self-measured plasma glucose measurements (SMPG) after 26 weeks: Mean pre-breakfast measurements used for titration
- Self-measured plasma glucose measurements (SMPG) after 38 weeks: Mean pre-breakfast measurements used for titration
- Self-measured plasma glucose measurements (SMPG) after 26 weeks: 9-point profile - Post-prandial increments
- Self-measured plasma glucose measurements (SMPG) after 38 weeks: 9-point profile - Post-prandial increments

Safety endpoints:

- Incidence of treatment-emergent adverse events (TEAEs) from baseline to week 26
- Incidence of treatment-emergent adverse events (TEAEs) during 38 weeks (defined as key supportive secondary safety endpoint in protocol)
- Incidence of treatment-emergent adverse events (TEAEs) during intensification period (week 26-38)

- Number of nocturnal, treatment-emergent severe or BG confirmed symptomatic hypoglycaemic episodes during 26 weeks
- Number of nocturnal, treatment emergent severe or BG confirmed symptomatic hypoglycaemic episodes during 38 weeks
- Number of nocturnal, treatment emergent severe or BG confirmed symptomatic hypoglycaemic episodes during maintenance (week 16-26)
- Number of treatment-emergent severe or blood glucose (BG) confirmed symptomatic hypoglycaemic episodes during 26 weeks (defined as key supportive secondary safety endpoint in protocol)
- Number of treatment-emergent severe or blood glucose (BG) confirmed symptomatic hypoglycaemic episodes during 38 weeks (defined as key supportive secondary safety endpoint in protocol)
- Number of treatment emergent severe or BG confirmed symptomatic hypoglycaemic episodes during maintenance (week 16-26)
- Total insulin dose at week 26
- Total insulin dose at week 38
- Change in weight from baseline to week 26
- Change in weight from baseline to week 38

Explorative endpoints

- Change from baseline to week 26 for:
 - Health-related quality of life as evaluated by SF-36v2® Health Survey
 - Treatment related impact as evaluated by the Treatment Related Impact Measure-Diabetes (TRIM-D)
- Change from baseline to week 38 for:
 - Health-related quality of life as evaluated by the SF-36v2® Health Survey
 - Treatment related impact as evaluated by the TRIM-D

Remaining endpoints in protocol version 4.0 are considered assessments.

Rationale:

Clarification on distinction between supportive secondary and exploratory endpoints.

3.4 Statistical analyses of the following assessments will not be performed

Efficacy assessments:

- $\text{HbA}_{1c} < 7\%$ without nocturnal (00:01-05:59) severe or BG confirmed symptomatic hypoglycaemia after 26 weeks
- $\text{HbA}_{1c} < 7\%$ without nocturnal (00:01-05:59) severe or BG confirmed symptomatic hypoglycaemia after 38 weeks

Safety assessments:

- Number of nocturnal, treatment-emergent severe or BG confirmed hypoglycaemic episodes during 26 weeks
- Number of treatment-emergent severe or BG confirmed hypoglycaemic episodes during 26 weeks
- Number of nocturnal, treatment-emergent severe or BG confirmed hypoglycaemic episodes during maintenance (week 16-26)
- Number of treatment-emergent severe or BG confirmed hypoglycaemic episodes during maintenance (week 16-26)
- Number of nocturnal, treatment-emergent severe or BG confirmed hypoglycaemic episodes during 38 weeks
- Number of treatment-emergent severe or BG confirmed hypoglycaemic episodes during 38 weeks

All above assessments will be summarized descriptively.

Rationale:

These assessments are supportive and no statistical analyses are needed.

3.5 Statistical analyses based on the secondary estimand will not be performed for the following endpoints

Efficacy endpoints:

- Change from baseline in FPG after 26 weeks
- Change from baseline in FPG after 38 weeks
- Change from baseline in mean pre-breakfast measurements after 26 weeks
- Change from baseline in post-prandial increments after 26 weeks
- Change from baseline in mean pre-breakfast measurements after 38 weeks
- Change from baseline in post-prandial increments after 38 weeks
- Responder (Yes/No) for $\text{HbA}_{1c} < 7\%$ after 26 weeks
- Responder (Yes/No) for $\text{HbA}_{1c} < 7\%$ without severe or BG confirmed symptomatic hypoglycaemia

- Responder (Yes/No) for $\text{HbA}_{1c} < 7\%$ after 38 weeks
- Responder (Yes/No) for $\text{HbA}_{1c} < 7\%$ without severe or BG confirmed symptomatic hypoglycaemia after 38 weeks

Safety endpoints:

- Change in weight from baseline to week 26
- Change in weight from baseline to week 38

Rationale:

For the above endpoints only the primary estimand are relevant.

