^h The baseline ECG must be performed at screening (V1) or in the period between screening (V1) and randomisation (V2). The result must be available prior to randomisation.
ⁱ ECGs before intensification (V28) and at the EOT visit (V40) should be performed at the day of the visit.

^j Dispense of 'washout' insulin products (BiAsp 30 or NPH + IAsp) to be used in the period between the EOT visit (V40) and the 7-day follow-up visit (V41) – Section [8.1.8](#).

^k The subjects must attend these visits fasting to collect FPG samples (Visits 2, 10, 14, 28, 34 and 40) and antibody samples (Visits 2, 6, 10, 14, 28, 40 & 41). Fasting is defined as at least eight hours without food and liquids, except for water. No diabetes treatment (neither trial insulin nor any oral antidiabetic treatment) is allowed up to eight hours prior to these measurements. Intake of other prescribed medicine is however allowed. If non-fasting, blood sampling should be re-scheduled, preferably within the next two working days.

^l Investigator or delegate staff will ensure proper training in trial product and pen handling. For subjects in the IGlar arm, the training must include pen differentiation. Directions for use (DFU) will be provided to the subjects. Hand-out of the DFU(s) to the subject must be documented in the subject's medical file. Re-training must be performed again at V3 and should be repeated during the trial based on the individual subject's needs.

^m At the EOT visit (V40) the subjects should be properly trained in how to handle 'washout' insulin products to be used in the period until the 7-day follow-up visit (V41). Handout of DFUs must be documented in the subject's medical file.

ⁿ Two follow-up visits are to be conducted. The first (V41) must take place no earlier than seven days and no later than 12 days after the EOT visit (V40). The last follow-up visit (P42) will take place approximately 30 days after the EOT visit (V40) and will be conducted as a phone contact (P42).

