8.1.5 Diaries

At each clinic visit, the subjects must receive diaries related to the following visit and/or phone contact(s). The diaries dispensed to subjects should be collected at the following clinic visit. However, for the screening visit (V1), the 30-days follow-up visit (P42) and the monthly phone contacts (in case of pre-term discontinuation of trial insulin products) no diaries will be provided.

The investigator should instruct subjects how to complete the diaries and ensure completion of these in accordance with the instruction provided.

Investigator or delegated staff must review data entered in the subject diaries, including PROs. Review of the diary and PROs must be documented either on the document and/or in the subject's medical record. If clarification of entries or discrepancies in the diary is needed, the subject must be questioned and a conclusion made in the subject's medical record. Care must be taken not to bias the subject.

It is the responsibility of the investigator to review the diary for subject's notes regarding possible AEs, hypoglycaemic episodes and concomitant medication, see Sections [12](#), [8.4.7](#) and [8.2.5](#).

Safety data from the diaries must be handled according to timelines described in Section [12.2](#).

The investigator or delegated staff should transcribe diary data into the eCRF as soon as possible after each site visit/phone contact. If necessary, the investigator should convert the format of data used by the subject into the format used in the eCRF.

Titration data should preferably be entered within 24 hours (refer to [Appendix A](#)). If data is obtained via phone and a discrepancy is later detected, the values in the eCRF should be corrected to the diary.

The investigator is only allowed to record the following data in the diary:

- Subject ID
- Site contact details
- Time and date of next visit or phone contact
- Prescribed dose(s) of trial insulin(s)
- Review signature

The subject must record the following information in the diary:

- Dates and doses of trial product injection, including first and last dose of trial product (V2-V40)
- Date, time and value of SMPG measurements used for weekly titration purposes (V2-V40)
- 9-point SMPG profile measurements including: date and actual clock time (V2, V18, V28, V34 and V40)
- Medical condition(s) including: hypoglycaemic episodes, other AEs, and potential change(s) in concomitant medication during the trial (V2-P41)

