8.1.11 Premature discontinuation of trial product

In case of premature discontinuation of trial product the investigator should make all effort to call the subject in for an unscheduled visit as soon as possible and must aim to undertake procedures similar to those for the EOT visit (V40), including fasting blood sampling and hand-out of ‘washout’ insulin products (refer to Section [5.3.3](#)) to be used in the period between the EOT visit (V40) and the 7-day follow-up visit (V41), where the last AB sampling will be performed.

Furthermore, the follow-up visits (V41 and P42) must be performed as described in Section [8.1.9](#).

For subjects prematurely discontinued from trial insulin products, monthly phone contacts (Px), as applicable, should be conducted after the 30-day follow-up (P42) and until the date where the EOT visit (V40) was originally planned to take place (38 weeks after Visit 2). Here an additional abbreviated visit 40 (V40a) should be performed. If the timing of a monthly phone contact is less than two weeks from a planned abbreviated visit, the phone contact can be omitted. If subject discontinues from trial product prior to Visit 28, an additional abbreviated visit 28 (V28a) should be scheduled at the date of the originally planned V28. At V28a and V40a HbA_{1c} samples and information of AEs and antidiabetic treatment will be collected, refer to the flow chart (Section [2](#)).

The primary reason for premature discontinuation of trial product must be specified in the ‘End of trial form’ in the eCRF, and final drug accountability must be performed. Furthermore, a treatment discontinuation session must be made in the IWRS.

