8.5.2.2 Fasting plasma glucose

FPG is analysed six times during the trial, and is measured in order to evaluate metabolic control. The subject must attend these visits fasting. For definition of fasting, see Section [8.1.4](#) above.

A FPG results ≤ 3.9 mmol/L (70 mg/dL) should not be reported as hypoglycaemic episode but as a clinical laboratory adverse event (CLAE) at the discretion of the investigator, see Section [12.1.1](#).

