2.1 Primary and secondary estimands

The primary estimand will be the difference in change from baseline at week 26 or week 38 depending on the endpoint considered between IDegAsp OD and IGlar OD + IAsp OD, for all randomised subjects regardless of whether the subjects remained on initially assigned treatment until week 26 or week 38. This estimand is a de facto estimand addressing effectiveness.

The secondary estimand will be the difference in change from baseline at week 26 or week 38 depending on the endpoint considered between IDegAsp OD and IGlar OD + IAsp OD if all randomised subjects had adhered to treatment until week 26 or week 38. This estimand is a de jure estimand addressing efficacy.

For hypoglycaemic episode endpoints, only the de jure estimand will be used. The reason for this is that data for hypoglycaemic episodes will not be systematically collected after treatment discontinuation.

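### SAP 3.5 keeps only the effectiveness estimand for FPG and SMPG, but the protocol text plans no FPG or SMPG at week 26 or 38 after premature discontinuation, so the analysis cannot estimate it

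*SAP*

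**What the plan says.** Protocol 17.5.1 planned analyses for both estimands for the continuous supportive efficacy endpoints. SAP 2.5.1 and 3.5 keep only the primary (de facto) one for FPG, mean pre-breakfast SMPG and post-prandial increments, each at weeks 26 and 38. The whole rationale is "For the above endpoints only the primary estimand are relevant". SAP 2.1 defines that estimand "for all randomised subjects regardless of whether the subjects remained on initially assigned treatment until week 26 or week 38".

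For subjects who stop trial product early, Protocol 8.1.11 provides abbreviated visits on the original week-26 and week-38 dates: "At V28a and V40a HbA_{1c} samples and information of AEs and antidiabetic treatment will be collected". Flow chart footnote o lists the same content, and amendment item 2.2 adds hypoglycaemic episodes. For the glucose measures:
- FPG: "FPG is analysed six times during the trial" (8.5.2.2). Footnote k names the occasions: "The subjects must attend these visits fasting to collect FPG samples (Visits 2, 10, 14, 28, 34 and 40".
- Titration SMPG, in the diary (8.1.5): "Date, time and value of SMPG measurements used for weekly titration purposes (V2-V40".
- The 9-point profile is left out even at the stopping visit (amendment items 2.2 and 2.9).

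At the time of stopping, the site is to "call the subject in for an unscheduled visit as soon as possible" (8.1.11), with procedures like those of V40, including fasting blood. Protocol 5.5 calls this same visit the EOT visit (V40).

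The supportive analysis reuses the imputation of SAP 2.4, done separately by arm, without the non-inferiority penalty (SAP 2.5.1).

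**The concern.** An estimate that holds regardless of adherence needs values at the landmark from subjects who no longer adhere. For HbA1c the plan retrieves them. For FPG and SMPG the protocol text does not, so the planned data can support an on-treatment estimate but not an effectiveness estimate. SAP 3.5 removes the first and reports the second.

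At stake is what may be concluded about fasting and post-prandial glucose. A reader of the trial report would take these differences as effects in all randomised subjects, including those who stopped, although nothing observed off treatment at the landmark informs them.

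**Working it through.** **1. What is planned after stopping**

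| Measure | Planned occasions | At week 26/38 after stopping |
|---|---|---|
| FPG | V2, 10, 14, 28, 34, 40 (footnote k) | Not listed for V28a or V40a (footnote o; 8.1.11; 8.5.2.1) |
| Pre-breakfast SMPG | Titration diary, V2 to V40 (8.1.5) | No diary for the monthly calls (8.1.5), which collect antidiabetic treatment and AEs (8.1.9), plus hypoglycaemic episodes (amendment 2.8) |
| Post-prandial increments | 9-point profile at V2, 18, 28, 34, 40 (8.1.5) | Not listed for V28a or V40a; also omitted at the stopping visit |
| HbA1c, for contrast | Regular visits | Sampled at V28a and V40a |

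The flow-chart assessment rows are not readable in the text available, so this rests on the footnotes and section text, which agree with each other.

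**2. What the imputation then estimates**

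The models in SAP 2.4 are fitted within arm on baseline factors and earlier values of the endpoint. They contain no term for treatment status, and for these endpoints no penalty follows. With no planned off-treatment landmark values, the regression is learned essentially from subjects still on treatment. Stoppers are imputed as if they had continued: MAR from on-treatment data.

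Week-38 FPG is the exception. SAP 2.4 uses planned visits, and 8.1.11 calls the stopping visit unscheduled, but Protocol 5.5 labels it V40. The SAP does not say how that sample is assigned. If it enters as V40, the last value near stopping is carried to week 38. That is LOCF-like, and also not de facto.

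**3. How many subjects**

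The plan's only related figure is N. With a one-sided 2.5% t-test, margin 0.40, adjusted difference 0.06, SD 1.3 and 85% power, I obtain 264 per arm, 528 in total (power 85.1%), as stated. SAP 2.2 assumes 15% stop or have missing data by week 26: 0.15 × 264 = 39.6 per arm. Protocol 6.1 expects 449 completers of 528: 528 − 449 = 79. Forty per arm is an upper figure, since the 15% includes data missing for other reasons. For week 26 only stops before V28 count.

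**4. Size of the error**

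Let d be an arm's stopping rate and s its off-treatment minus on-treatment shift at the landmark (1 = IDegAsp, 0 = comparator). The de facto arm mean is the on-treatment mean plus d × s, so the MAR estimate misses the de facto difference by

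d1 × s1 − d0 × s0.

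Illustrations for FPG, with every s and every arm split assumed:
- 15% in both arms, equal s: 0.
- 15% in both arms, s = 2 and 1 mmol/L: 0.15 × (2 − 1) = 0.15.
- 20% and 10%, s = 1 in both: 0.20 − 0.10 = 0.10.
- 15% in both arms, an on-treatment difference of −0.5 that vanishes after stopping: de facto 0.85 × (−0.5) = −0.425, a gap of 0.075.

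A simplified simulation (264 per arm, 600 replicates, 10 imputations, no values after stopping) agrees. For the last case, imputation gave −0.48 against a de facto −0.41. With no on-treatment difference, 20% IDegAsp and 10% comparator stopping and a shift of +1.0, it gave −0.01 against +0.09 (Monte Carlo SE 0.007). The shifts were built in, so this confirms the mechanism and not the magnitude.

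**The case against.** **Subjects are asked to stay and complete everything.** Protocol 6.6 does ask this, but it refers those who stop to 8.1.11, which sets the abbreviated content. A general request does not create an FPG sample at V28a.

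**The change is declared and concerns supportive endpoints only.** Both are true, and they limit the importance of the point. They do not supply the missing data.

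**The remedy leaves the gap in place.** This stands. The MMRM also assumes MAR and may be numerically close to the imputation. A reader might infer that restoring it removes the error in step 4; it does not. It makes the label match the data.

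Other stronger readings that the documents do not support:
- *That the FPG and SMPG differences are biased by a known amount.* The documents give no shift and no arm split, and stoppers in both arms receive alternative therapy at the investigator's discretion, so no asymmetry is indicated.
- *That the result is MAR in every case.* Week-38 FPG depends on the unstated handling of the stopping-visit sample.
- *That hypoglycaemia sets an exact precedent.* SAP 2.1 restricts it to the de jure estimand because "data for hypoglycaemic episodes will not be systematically collected after treatment discontinuation". The reasoning is relevant, but the amendment now collects episodes at V28a, V40a and the monthly calls, so the gap there is narrower than for FPG and SMPG.
- *That weight or the HbA1c responders share the problem.* The timing of weight lies in flow-chart rows that cannot be read here, and off-treatment HbA1c is retrieved.

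**Conclusion.** The point holds for six supportive endpoints: change in FPG, mean pre-breakfast SMPG and post-prandial increments, each at weeks 26 and 38. As planned, they would be reported as effectiveness while resting on MAR from on-treatment data or, possibly for week-38 FPG, on an LOCF-like value. Neither is the estimand in SAP 2.1.

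About 15% of subjects, up to 40 per arm, would lack a landmark value. The error in the difference is d1 × s1 − d0 × s0, and its value cannot be fixed from the documents. The conclusion assumes that the unreadable flow-chart rows agree with the footnotes and sections 8.1.11 and 8.5.2.

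The primary non-inferiority analysis, the 38-week HbA1c change (both estimands kept, off-treatment values retrieved) and N = 528 are unaffected.

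**What to change.** 1. Restore the on-treatment MMRM of Protocol 17.5.1 for the six endpoints and report it as the efficacy estimand.
2. If the imputation is kept, describe it as resting on MAR from on-treatment data and draw no effectiveness conclusion from it. Alternatively, add a departure-from-MAR (delta) sensitivity analysis, like the tipping point already planned for HbA1c in SAP 2.4.
3. State that FPG from a premature stopping visit is not analysed as the V28 or V40 landmark value.

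The cost is SAP wording and six runs of a model the protocol already specified, plus the delta analysis if chosen. No protocol amendment and no new data are needed. The downside is that these endpoints would carry a different estimand label from the primary endpoint.

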3.6 Changes to reporting of safety end points related to adverse events

Below mentioned end point is added:

- Incidence of treatment-emergent adverse events (TEAEs) during intensification period (week 26-38)

Rationale:

Safety when intensifying from OD to BID/TID is of interest for the trial.

The following sentence of protocol 4.0 will be deleted: “The EAC confirmed adverse events will be listed and summarised descriptively.”

Rationale:

Included in protocol by mistake, as no adjudication is done.

